7.3 LOST TO FOLLOW-UP

A participant will be considered lost to follow-up if he or she fails to comply to weekly surveys, misses exit appointment, and is unable to be contacted by the study site staff.

The following actions must be taken if a participant fails to return to the clinic for the final study visit:

- The site will attempt to contact the participant and reschedule the exit appointment and counsel the participant on the importance of maintaining the assigned visit to return equipment and debrief (whether or not the participant chooses to complete exit surveys).
- Before a participant is deemed lost to follow-up, the investigator or designee will make every effort to regain contact with the participant (where possible, 3 telephone calls and, if necessary, a certified letter to the participant's last known mailing address or local equivalent methods). These contact attempts should be documented in the participant's study file.
- Should the participant continue to be unreachable, he or she will be considered to have withdrawn from the study with a primary reason of lost to follow-up.

8.1 EFFICACY ASSESSMENTS

PROMIS[®] Questionnaires

The primary outcome for this study will be self-reported physical function (PF) using the PROMIS® PF short form scale. For patients with acute pain, PF is often diminished and patients seek return to normal function. The PROMIS® PF short-form scale is a widely- validated instrument with excellent content validity, construct validity, and reliability in patients with spinal disorders and other conditions marked by diminished mobility. The instrument place patients on a continuum of function from extremely low to very high across activities that require physical actions, ranging from self-care to more complex activities that require a combination of skills. The scale is rendered using a T-statistic, where a score of 50 represents the population mean, and 10 points is a standard deviation (SD). The minimally clinically important difference (MCID) on the PROMIS® PF short form is 2 points, or 0.2 SD. [22]

Secondary outcomes will include the PROMIS[®] pain interference scale and the PROMIS[®] global health scale. The pain interference scale measures the consequences of pain on relevant aspects of one's life. This includes the extent to which pain hinders engagement with social, cognitive, emotional, physical, and recreational activities. The PROMIS[®] global health scale is an overall evaluation of one's physical and mental health. We will include this instrument to address outcomes that are not often addressed in pain interventions, including fatigue and mental health. All PROMIS[®] measures use a 7-day recall period reflecting the previous week's health status.

To collect the patient reported outcomes (PROs) for this study, we will use ecological momentary assessment (EMA) software (LifeData), a HIPAA-compliant, cloud-based survey administration platform capable of administering surveys in real-time. We will also allow patients use Redcap as an alternative program to collect PROs. With this program the patient doesn't have to use an app on their phone and instead just respond to surveys sent to their email address. To administer PROs, we will upload a list of patient email addresses into their HIPAA-compliant website which in turn allows scheduled administration of PRO questionnaires at daily and weekly intervals. Each week, the EMA app will send patients a reminder to fill out the scheduled PROs. If they do not fill them out, they will be sent a reminder prompt. The data collected by LifeData or Redcap will then be downloaded into a secure analysis and visualization file accessible to the research team and the Digitalist.

Work Productivity and Activity Impairment

Work productivity can be measured in terms of absenteeism (missing work) and presenteeism (diminished productivity at work). The Work Productivity and Activity Impairment (WPAI) questionnaire is a validated, widely used, brief, 6-item questionnaire that measures absenteeism and presenteeism related to specific health conditions.

Use of Opioids

In order to capture medication use related to their injury, including the use of opioids, we will link patient electronic health record (EHR) data to the other data sources using Medical Record Numbers and date of birth. We will collect opioid prescription information using pharmaceutical claims data, and also collect information on medications commonly used by individuals with chronic pain conditions. Prescribed opioid medications include: codeine, dihydrocodeine, tramadol, morphine, hydromorphone, oxymorphone, tapentadol, buprenorphine, methadone, oxycodone, fentanyl, remifentanil. We will convert all opioid doses into a single metric using morphine milligram equivalents (MME).

Satisfaction with Pain Treatment and Healthcare Surveys

We will evaluate patient experience data as measured by the 39-item Pain Treatment Satisfaction Scale and the 18-item short-form version of the Patient-Satisfaction Questionnaire. Both questionnaires are validated for use in studies to compare patient satisfaction between different treatment assignments.

Use and satisfaction with the TENS device will be monitored via daily questionnaires administered by either LifeData or Redcap (as described above).

8.2 SAFETY AND OTHER ASSESSMENTS

Safety will be monitored by following up with participants for any adverse events (AE), assessment of adherence by support staff, and monitoring of biometric information and questionnaires by the digitalist.

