5.5 STRATEGIES FOR RECRUITMENT AND RETENTION

Male and female participants above the age of 18 will be screened to reach target enrollment 174 patients over a period of 16 months. Participants presenting with pain due to a musculoskeletal injury will be screened and enrolled at four sites (Cedars Sinai Orthopedic Clinic, Medical Delivery Network, Cedars Sinai Pain Management Clinic, Medical College of Wisconsin). Patients will be identified and approached by their providers. The treating physicians will contact their patients during their clinic visits and assess the patient's willingness to be contacted about the research and the treating physician will document the patient's willingness to be contacted on the *CSMS Research Interest* letter. The Research Letter will be tailored to each clinical practice of the treating provider. Additionally, participating providers will distribute recruitment pamphlets to patients in clinic and/or through mail. Should the patient be interested in being contacted about the study, the study team will then approach the patient for

participation in the research either in person or over-the-phone. The patient will have the option to complete their consent forms on paper or electronically using the 21 CFR 11-compliant online platform, DocuSign. Every subject will be informed of the approximate time to complete the consent process. Consenting will be done with a research staff member either in-person or remotely via DocuSign to ensure the identity of the person signing the informed consent form is indeed the subject participating in the research study. A copy of the informed consent documents will be given to the participants for their records via their email or a physical hard copy. Participants who consent remotely will receive their study equipment through a secure FedEx package requiring a signature. Retention to the 60-day study for the intervention group will be managed using weekly reminders to complete survey protocols, as well as optional opt-in monitoring of compliance and health data via remote clinical and technical support staff. Participants will not receive monetary compensation for participating in this study.

Participants experiencing lower back pain will be oversampled to a minimum of 45 per arm in order to obtain sufficient sample size for testing the success of the TENS unit.

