In the current study, we will simulate aspects of the Health Coach model by allowing patients in the intervention arm to remotely share their secure mHealth data with selected members of the research team. VR usage data will also be transmitted remotely through the appliedVR app, allowing our team to monitor adherence with the VR intervention. We will assign two staff to monitor patients in the control arm: (1) technical support staff member, and (2) Health Coach. Patients will receive a telephone number and email to contact support staff as needed. The technical support staff will also reach out if there is low adherence with the devices, prolonged missing wearable data, or low battery power detected on the remote monitoring dashboard. The Health Coach will reach out if there is evidence of worsening physiologic or activity parameters (e.g. walking less, sleeping less, heart rate increasing) using their clinical judgment. Patients will be informed to contact 911 and/or call their physician directly if they experience any urgent, semi-urgent, or concerning signs or symptoms. The Health Coach will check mHealth data logs twice weekly on weekdays, and contact the patient by phone according to the patient's stated preferences. Patients who do not want Health Coach remote monitoring will not receive this component of the intervention but will still be included in the intention-to-treat population.

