6.1.2 DOSING AND ADMINISTRATION

Participants are assigned TENS devices and VR to be used as needed. Participants are also instructed to use VR at least three times a day. The dosage for both devices will not change throughout the study. Individuals assigned to remote monitoring will be continuously monitored and any action will be physician-initiated. Participants in the control group will receive standard of care and TENS unit.

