7 STUDY INTERVENTION DISCONTINUATION AND PARTICIPANT DISCONTINUATION/WITHDRAWAL

7.1 DISCONTINUATION OF STUDY INTERVENTION

Discontinuation from the use of the digital pain reduction kit does not mean discontinuation from the study, and remaining study procedures should be completed as indicated by the study protocol. If a clinically significant finding is identified (including, but not limited to changes from baseline) after enrollment, the investigator or qualified designee will determine if any change in participant management is needed. Any new clinically relevant finding will be reported as an adverse event (AE).

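### Recorded adverse-event counts may partly reflect unequal looking: the follow-up common to all groups has no set timing or wording, and coach, biometric and VR-adherence monitoring sits mainly in the kit arm.

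*Combined protocol and SAP*

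**What the plan says.** Section 8.2 is a single sentence. It names three channels: "following up with participants for any adverse events (AE), assessment of adherence by support staff, and monitoring of biometric information and questionnaires", the last by the digitalist. It does not say when participants are asked, in what words, or by whom.

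Section 7.1 gives the reporting rule: "Any new clinically relevant finding will be reported as an adverse event (AE). It is not limited to one arm, and the findings it covers expressly include changes from baseline.

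Monitoring beyond this is described mostly for the kit arm:

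- The intervention description in section 1.1 lists remote clinical and technical support as a kit component, and section 6.1.1 repeats it. The synopsis denies controls VR and coaching.
- Section 5.5 says that retention "for the intervention group will be managed using weekly reminders to complete survey protocols, as well as optional opt-in monitoring of compliance" and health data.
- Section 6.1.1, under the heading on the Health Coach model in the intervention arm, has kit patients share mobile health data, with two log checks a week. It adds: "The Health Coach will reach out if there is evidence of worsening physiologic or activity parameters". Technical staff make contact when device use is low.
- Section 6.1.2 says: "Individuals assigned to remote monitoring will be continuously monitored". It then describes controls as having standard care and TENS.

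Coach monitoring is optional: "Patients who do not want Health Coach remote monitoring will not receive this component of the intervention".

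Some data reach controls as well. PROMIS questionnaires are weekly in section 1.3, and in section 8.1 "Use and satisfaction with the TENS device will be monitored via daily questionnaires", with no arm limit. Section 8.1 also gives the digitalist access to the survey data of patients generally.

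**The concern.** The events at issue are general worsening, which can happen in any group. In a kit patient who accepts monitoring, falling activity or low device use can prompt a call, and what emerges on the call can be recorded as an adverse event. A control has no comparable contact described. The same worsening there has to surface through a questionnaire, a visit, a spontaneous report, or follow-up whose timing is not set.

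If one arm is watched more closely, its count rises even when true risk is equal, and a later table cannot undo unequal collection. The trial is open label (section 6.2), so blinding offers no protection. The counts still matter: section 2.3.3 makes a benefit-risk judgement, section 10.1.2 allows suspension for unacceptable risk, and section 10.1.6 commits to reporting results.

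**Working it through.** The plan gives no adverse-event rate, target or comparison to reproduce, so the check sets the sections side by side and counts contacts.

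**Schedule rows (section 1.3).** Consent, demographics, history, randomization, EHR data, kit administration, VR, TENS, PROMIS, WPAI, satisfaction, VR compliance, remote support, kit collection: 14 rows, 0 for adverse events. Section 9 contains no harm summary.

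**Contacts per participant over 60 days.**

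- PROMIS: Visit 1, eight weekly points from Day 7 to Day 56, and Day 60, so 1 + 8 + 1 = 10.
- Coach log checks: 2 per week × 60/7 weeks = 17.1, about 17, only for kit patients who accept.
- Daily TENS questionnaire: up to about 60 for anyone with a device.

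| Channel | Kit | Control with TENS | 24 controls without TENS | An adverse-event question? |
|---|---|---|---|---|
| Adverse-event follow-up (8.2) | yes, timing not set | same | same | wording not given |
| Site visits (1.3) | 2 | 2 | 2 | not stated |
| PROMIS (1.3) | 10 | 10 | 10 | no |
| Daily TENS survey (8.1) | up to about 60 | up to about 60 | presumably none | no; use and satisfaction |
| Coach log checks (6.1.1) | about 17 if accepted | none described | none described | no |
| VR-use data (6.1.1, 6.3) | yes | not applicable | not applicable | no |

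The table assumes that the 24 controls without TENS followed the same visit and PROMIS schedule.

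**Reading the table.** No row is a defined adverse-event question. The rows that differ between kit and control with TENS are coach checks and VR-use data, with the contact that either may prompt. The 24 controls without TENS also lack the daily device survey.

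**Which events are exposed.** General worsening is. TENS symptoms are less so, because activity and VR-use logs would not show them and the daily survey has no arm limit. VR discomfort arises only with the kit, so it is not a between-arm matter.

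**A contrary sentence.** Section 6.1.1 also says: "We will assign two staff to monitor patients in the control arm". It stands under the intervention-arm heading and conflicts with the synopsis and the rest of section 6.1.1, so I read it as a slip. Taken literally, monitoring would still be unequal, but the likely direction would no longer be clear.

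**The case against.** The strongest reply is that the plan does not confine safety surveillance to one arm, and most of that reply stands.

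- A reader might infer that a control's decline on PROMIS could never become an adverse event. The documents do not support this. The section 7.1 rule has no arm limit and includes changes from baseline, section 8.2 names questionnaire monitoring as a safety channel, and section 8.1 gives the digitalist the data. No numeric threshold is set, but none is set for kit-arm activity data either.
- Section 6.1.2 makes any action from remote monitoring a physician's to start, whereas the synopsis and section 6.1.1 have the coach initiate contact. The path from a log entry to a recorded event is less direct than section 6.1.1 alone suggests.
- The amount of biometric data is uncertain. Section 6.1.1 lists two kit devices and no wearable, though it later mentions wearable data, and section 10.1.3 refers to real-time biometrics without an arm limit.
- The synopsis says in general terms that patients get remote clinical and technical support, so controls may have some. Survey logs are a compliance source in every group (section 6.3).
- No harm comparison is an objective in section 3.

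What remains is that shared access to data is not the same as asking everyone the same question at the same times. Coach contact prompted by logs is described for the kit arm, and the common follow-up is too loosely specified to show that ascertainment is equal.

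**Conclusion.** The point holds as a minor weakness in safety data collection. Under the plan as written, adverse-event counts by arm may reflect unequal looking, probably towards more recorded events in the kit arm.

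It rests on three assumptions: the sentence about the control arm is a slip, some kit patients accept coach monitoring, and the health data described in section 6.1.1 are in fact collected. If nobody opts in, or no such data exist, most of the difference disappears.

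A reader might go further and conclude that the counts are shown to be biased, or that the bias is large or small enough to settle whether a false significant difference would arise. The documents support neither. They give no event rate, no opt-in share and no detection probabilities, so any ratio would depend wholly on assumed inputs. No planned efficacy analysis is affected.

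**What to change.** Ask one identically worded adverse-event question in all groups, at Visit 2 at minimum and in the existing weekly survey if burden allows. Add it as a row in section 1.3. Record how each event was found: common question, visit, spontaneous report, or coach or support contact. Base any comparison between arms on events found by the common question or at a visit, and list coach- and support-found events separately. Report the 24 controls without TENS descriptively; even with no events among 24, the exact two-sided 95% upper limit is 1 − 0.025^(1/24) = 14.2%.

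The cost is one question, one schedule row and one source field, with no extra visits or patients. There are three downsides:

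- Survey burden rises slightly, which matters because the summary of changes attributes withdrawals to low survey compliance. Asking only at Visit 2 avoids most of this but relies on longer recall.
- Participants who finished before the change have only unstandardised data and should be shown separately.
- Adherence outreach may still raise survey response in the kit arm, so response to the question should be shown by arm.

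Two drafting points can be settled at the same time: correct the section 6.1.1 sentence about the control arm, and state in the synopsis whether controls receive technical support.

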9 STATISTICAL CONSIDERATIONS

9.1 STATISTICAL HYPOTHESES

• Primary Efficacy Endpoint(s):

Primary Outcome: Physical function over time as measured by PROMIS PF score (T- Scored, Continuous)

Question: Which intervention is more effective in improving physical function?

Independent variable of interest: Comparator received, intervention vs. control (Dichotomous)

Potential Covariates: Age, gender, race, ethnicity, mental health comorbidities, chronic pain diagnosis, use of other pain medications (neuropathic pain medications, NSAIDS, antidepressants), benzodiazepine use, number of office visits during study period, baseline PROMIS[®] scores, encounter month, physician years of practice, physician gender.

• Secondary Efficacy Endpoint(s):

Secondary Outcome: Pain over time as measured by PROMIS Pain Interference Score (T-Scored, Continuous)

Question: Which intervention is more effective in improving patient's pain interference?

Independent variable of interest: Comparator received, intervention vs. control (Dichotomous).

Potential Covariates: Same as Primary Aim.

Secondary Outcome: Effects of lower back pain symptom severity on work productivity and regular activities over time as measured by WPAI:LB (T-Scored, Continuous).

Question: Which intervention is more effective in improving patient's work productivity and participation in regular activities?

Independent variable of interest: Comparator received, intervention vs. control (Dichotomous).

Potential Covariates: Same as Primary Aim.

Secondary Outcome: New Opioid Prescription over 90MME (Dichotomous)

Question: Which intervention is more effective in reducing opioid prescriptions of 90 Morphine Milligram Equivalents (MME) or greater?

Independent variable of interest: Comparator received, intervention vs. control (Dichotomous).

Potential Covariates: Same as Primary Aim.

Statistical Analyses: As in the primary aim analyses, we will employ mixed effects models featuring both fixed effects and random effects to account for within subject variation.

Because this particular outcome is binary, we will use mixed logistic regressions in which the log odds of the outcomes are modeled as a linear combination of the predictors.

Secondary Outcome: Satisfaction with Pain Treatment and Healthcare Scores

Question: Which intervention is more effective in improving how satisfied patients feel with their care?

Dependent variable: Pain Treatment and Patient Satisfaction Scores

Independent variable of interest: Comparator received, intervention vs. control (Dichotomous)

Potential Covariates: Same as Primary Aim.

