1.3 SCHEDULE OF ACTIVITIES (SOA)

Procedures	Screening Day -7 to -1	Visit 1, Day 1	Day 7 +/-1 day	Day 14 +/- 1 day	Day 21 +/-1 day	Day 28 +/-1 day	Day 35 +/-1 day	Day 42 +/-1 day	Day 49 +/-1 day	Day 56 +/-1 day	Final Study Visit 2 Day 60 +/-1 day
Informed consent	Х										
Demographics	Х										
Medical history	Х										
Randomization	Х										
EHR data (opioid use)		Х									Х
Administer study intervention kits		Х									
Intervention (Virtual reality)		Х	Х	Х	Х	Х	Х	Х	Х	Х	Х
Intervention (TENS)		Х	Х	Х	Х	Х	Х	Х	Х	Х	Х
PROMIS [®] questionnaires		х	х	х	х	х	х	х	Х	х	Х
Assess absenteeism and presenteeism (WPAI)		Х									х
Satisfaction with pain treatment and healthcare											Х
Collect VR compliance data		Х									Х
Remote clinical and/or technical support X				Х							
Collect study intervention kits											Х

Note: Participants will only have two site visits, the SoA illustrates additional days for remote measurement. Site visit days are labeled as "Visit 1" and "Visit 2."

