One answer for moving digital health forward is to develop a new type of specialist called the "Digitalist."[20] The Digitalist does not yet exist at scale, just as "The Hospitalist" did not exist prior to 1996, when Robert Wachter and Lee Goldman coined the term to describe a much-needed clinician to fill an unmet need for inpatient care.[21] Now we have an unmet need for a new clinician (though not necessarily a physician), trained in digital health, who will monitor, interpret, and act upon remote patient data – in this instance among patients recovering from a low back injury. In this study, a health coach, acting similar to a Digitalist, will remotely track data from biosensors, portals, and apps, then combine the data to provide guidance with adhering to the intervention.

Patients transmit actively and passively collected data through apps and portals. The Digitalist monitors the data, and, if needed, contacts the patient via EHR portal, telephone, or videoconferencing. If appropriate, the Health Coach communicates directly with clinicians, informs them of updates, and coordinates the optimal timing of in-person visits. The clinician may also access digital health reports, review the results with the patient, and make further decisions based on the data coupled with the traditional history and physical examination.

This model has potential to expand care beyond the traditional clinic visit, uses visits more effectively, reduces avoidable admissions, and improves outcomes of care.

Implementation of Health Coach Model in Intervention Arm

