9.4.2 ANALYSIS OF THE PRIMARY EFFICACY ENDPOINT(S)

Statistical Analyses: Data for Aim 1 are repeated-measures data and will not support bivariate analysis by Pearson and/or Spearman correlations, as autocorrelation can cause transient or spurious relationships with high correlations for some periods and none for others. Similarly, for a linear regression model, this type of data may cause residuals for the same individual to be correlated. Therefore, we will employ linear mixed models featuring fixed effects and random effects (i.e. random intercepts) to account for within subject variation. We will also perform a differences-in-differences analysis comparing change between baseline and the end of the intervention to determine which strategy resulted in greater improvement in PF.

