9.4.3 ANALYSIS OF THE SECONDARY ENDPOINT(S)

Statistical Analyses: As in the primary aim analyses, we will employ linear mixed models featuring fixed effects and random effects to account for within subject variation. We will also perform a differences-indifferences analysis comparing change between baseline and the end of the intervention to determine which strategy resulted in greater improvement in PF.

Statistical Analyses: As in the primary aim analyses, we will employ linear mixed models featuring fixed effects and random effects to account for within subject variation. We will also perform a differences-indifferences analysis comparing change between baseline and the end of the intervention to determine which strategy resulted in greater improvement in PF. Statistical Analyses: In addition to unadjusted comparisons, we will employ multiple linear regression models.

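### Section 9.1 offers a post-randomisation count of office visits as a covariate for the primary outcome and all four secondary outcomes listed there

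*Combined protocol and SAP*

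**What the plan says.** Section 9.1 gives one list of potential covariates for the primary outcome, PROMIS physical function. Besides baseline characteristics and baseline PROMIS scores it contains "number of office visits during study period". Each of the four secondary outcomes in that section then has the line "Potential Covariates: Same as Primary Aim". These are pain interference, WPAI:LB, a new opioid prescription over 90 MME, and satisfaction.

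The Schedule of Activities (Section 1.3) puts randomisation in the column "Screening Day -7 to -1". Kits are issued on Day 1 and follow-up runs to Day 60.

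Section 9.4.2 plans linear mixed models with random intercepts, without naming covariates, and a "differences-in-differences analysis comparing change between baseline and the end of the intervention". Section 9.4.3 repeats this for secondary endpoints and ends, apparently for satisfaction, with "In addition to unadjusted comparisons, we will employ multiple linear regression models". Section 9.1 plans mixed logistic regression for the opioid outcome. Sections 9.3 and 9.4.4 commit to intention-to-treat analysis by assigned arm.

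**The concern.** A count that accrues after randomisation can be a consequence of treatment. Conditioning on it removes any part of the effect that runs through visits. It also links arm to unmeasured severity, because patients with the same visit count in different arms need not be alike. Either way, the comparison that randomisation protects is lost.

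The documents give reasons why arm could affect visits:

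- Section 6.1.1 says that in the coaching model the coach "coordinates the optimal timing of in-person visits" and that the model "uses visits more effectively". The synopsis says controls get no remote coaching. One sentence in 6.1.1 places the support staff in the control arm, against its own subheading and the synopsis; I follow the synopsis.
- Section 6.1.1 offers an in-person session to patients who cannot work the VR device at home. Only the intervention arm has VR. Whether such a session counts as an office visit is not stated.
- Section 6.2 says the trial is unblinded, so knowing the assignment may change care-seeking.

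At stake is whether the reported arm effect answers the intention-to-treat question for the primary outcome and four secondary outcomes.

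**Working it through.** **Timing.** Randomisation falls on Day -7 to -1. The participant period is 60 days. A count over the study period is therefore known only after randomisation.

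**Is it removed elsewhere?** No. Sections 9.4.2 and 9.4.3 neither exclude it, restrict it to earlier visits, nor give a rule for choosing covariates. The equation in 9.4.4 contains only time, arm and TENS, but it is an additional analysis.

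**Size.** The plan states no figure to reproduce. The only documented input is the 0.60 SD effect in Section 9.2; everything else is assumed. Work in within-arm SD units, with:

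- d = mean visits, intervention minus control
- r_vy = visit-outcome correlation
- r_vb = visit-baseline correlation
- r_by = baseline-outcome correlation, set to 0.6

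With arm, baseline and visits in the model, the visit coefficient is g = (r_vy - r_by × r_vb)/(1 - r_vb²), and the adjusted arm effect is 0.60 - g × d.

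For example, r_vy = -0.4 and r_vb = -0.3 give g = (-0.4 + 0.18)/0.91 = -0.242. At d = -0.5 the effect is 0.60 - 0.121 = 0.48; at d = +0.5 it is 0.72; at d = 0 it stays 0.60.

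Absolute shift in SD:

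| r_vb | g (r_vy = -0.4) | shift, d = ±0.5 | shift, d = ±0.2 | g (r_vy = -0.2) | shift, d = ±0.5 |
|---|---|---|---|---|---|
| 0 | -0.400 | 0.20 | 0.08 | -0.200 | 0.10 |
| -0.2 | -0.292 | 0.15 | 0.06 | -0.083 | 0.04 |
| -0.3 | -0.242 | 0.12 | 0.05 | -0.022 | 0.01 |
| -0.4 | -0.190 | 0.10 | 0.04 | +0.048 | 0.02 |

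Simulation agrees. With 200,000 per arm, r_vy = -0.4 and r_vb = -0.3, the adjusted effect was 0.480, 0.600 and 0.722 at d = -0.5, 0 and +0.5. A random-intercept model with nine post-baseline assessments and 1,500 per arm moved from 0.576 to 0.475, from 0.584 to 0.591, and from 0.602 to 0.728 when visits were added.

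**No true effect.** A second illustration has no baseline term. Unmeasured severity raises visits (path 0.5) and lowers the outcome (path -0.5), and visits do not affect the outcome. The within-arm slope is 0.5 × (-0.5) = -0.25. With a true effect of 0, the adjusted estimate is 0 - (-0.25)(-0.5) = -0.125 when the intervention lowers visits by 0.5 SD, and +0.075 when it raises them by 0.3 SD. Simulation gave -0.120 and +0.079. A null effect can thus look non-null.

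**Difference-in-differences.** In a long-form model, a visit count that is constant within person and entered as a main effect leaves the arm-by-period term unchanged (0.602 with and without it in simulation). If change scores are regressed on arm and visits, g = r_vy - r_vb. With r_vy = -0.4 and |d| = 0.5 the shift is 0.20, 0.10, 0.05 or 0 SD for r_vb = 0, -0.2, -0.3 or -0.4.

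**Opioid outcome.** Assume an odds ratio of 0.50 and 0.4 log-odds per SD of visits. Ignoring non-collapsibility, the adjusted odds ratio is about 0.50 × exp(-0.4d): 0.61 at d = -0.5 and 0.41 at d = +0.5. Ordinary logistic simulation gave 0.611, 0.498 and 0.405 at d = -0.5, 0 and +0.5, against 0.504, 0.503 and 0.501 without visits. The plan's mixed logistic model was not simulated.

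**The case against.** The strongest reply is that nothing shows visits will be used. The list is only of potential covariates, 9.4.2 names none, and the one equation written out (9.4.4) leaves visits out. This is true, but with no selection rule the plan permits the adjustment and leaves the choice open until data are in hand.

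Second, 9.4.2 does not say whether the primary contrast is arm or arm-by-time. With complete data, an arm-by-time term would be unaffected by a person-level visit count entered as a main effect. That stands and narrows the exposure. However, the equation in 9.4.4 treats the arm main effect as the term of interest, which is the exposed form.

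Third, an arm difference in visits is conjecture. Section 6.1.1 says "we will simulate aspects of the Health Coach model", contact is mainly by phone, patients may decline it, and the scheduled site visits are the same in both arms. This also stands: the documents do not show that visits will differ. But that cannot be known when the plan is fixed, and the plan should not depend on it.

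Fourth, the first PROMIS assessment is on Day 1, also after randomisation. The relevant line is therefore whether a covariate can be affected by the intervention. A baseline score taken before the kit is used meets that test; a 60-day visit count does not.

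For satisfaction, an unadjusted comparison appears to be planned as well, so an estimate free of visits would be available there.

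**Conclusion.** The point holds. Section 9.1 lists a post-randomisation count as a potential covariate for the primary outcome and four secondary outcomes, and no later section withdraws it. The effect on this trial's results is conditional: it needs visits to differ by arm and to relate to the outcome, and it needs the arm main effect (or a change-score regression) to be the reported contrast.

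Under the assumed inputs, the shift in the baseline-adjusted effect runs from 0 to 0.20 SD, in either direction. The middle case of 0.12 SD is about 1.2 T-score points if the SD is the 10 points given in Section 8.1. That is 60% of the 2-point MCID stated there (1.2/2). This is worth correcting before analysis; it does not undermine the design.

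**What to change.** Delete the visit count from the covariate list in Section 9.1 for all outcomes, and keep the baseline PROMIS score. Report office visits by arm descriptively, or as an outcome.

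A secondary clarification, not a separate error: the list gives no time point for pain-medication and benzodiazepine use. State that these mean use up to Day 1, before kits are issued, or drop them if that cannot be obtained.

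The main change is one deleted phrase, with no new data, visits or patients. Reporting visits by arm uses counts the plan already assumes it will have. The medication clarification costs one sentence and a check that use up to Day 1 is available from the screening history or the EHR.
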